13.1.1 Grading of adverse events

Grade refers to the severity of the AE. CTCAE (Version 5.0, released on 27-Jul-2017) displays Grades 1 through 5 with unique clinical descriptions of severity for each AE based on the following basic criteria:

CTCAE grading

Grade	Clinical description
Grade 1	Mild; asymptomatic or mild symptoms; clinical or diagnostic observations only; intervention not indicated.
Grade 2	Moderate; minimal, local or noninvasive intervention indicated; limiting age-appropriate instrumental ADL*.
Grade 3	Severe or medically significant but not immediately life-threatening; hospitalization or prolongation of hospitalization indicated; disabling; limiting self-care ADL**
Grade 4	Life-threatening consequences; urgent intervention indicated.
Grade 5	Death related to AE.
Remarks	
A semi-colon indicates 'or' within the description of the grade. A single dash (-) indicates a Grade is not available. Not all Grades are appropriate for all AEs.
 
Activities of Daily Living (ADL):
 
* Instrumental ADL refer to preparing meals, shopping for groceries or clothes, using the telephone, managing money, etc.
 
** Self-care ADL refer to bathing, dressing and undressing, feeding self, using the toilet, taking medications, and not bedridden.

13.1.2 Report and handling of AEs

All AEs observed during the trial must be truthfully recorded in the adverse event form. Investigator should carry out targeted treatment and follow-up to AEs until symptoms disappear or become stable.

13.1.3 Determination of the relationship between AE and test product and operation

The subject should evaluate the correlation between the AE and test device or operation, and classify according to the following criteria:

(1) Correlation with test device

- 1) Definitely relevant: The reaction conforms to the known reaction type of the suspected product.
- 2) Possibly related: The reaction conforms to the known reaction type of the suspected product; The patient's clinical status or other treatment methods may also produce this reaction.
- 3) Possibly irrelevant: The reaction does not quite conform to the known reaction type of the suspected product; The patient's clinical status or other treatment methods may produce this reaction.
- 4) Definitely irrelevant: The reaction does not conform to the known reaction type of the suspected product; The patient's clinical status or other treatment methods may produce this reaction, and the disease state may be improved or the reaction may be eliminated by withdrawal of other treatment methods, and present again upon the repeated use of other treatment methods.
- 5) Unable to judge: The reaction is similar to the known reaction type of the suspected product, and other treatments used at the same time may also cause the same reaction.

(2) Correlation with operation

- 1) Definitely relevant: The reaction conforms to the known reaction type of the operation.
- 2) Possibly related: The reaction conforms to the known reaction type of the operation; The patient's clinical status or other treatment methods may also produce this reaction.
- 3) Possibly irrelevant: The reaction does not quite conform to the known reaction type of the operation; The patient's clinical status or other treatment methods may produce this reaction.
- 4) Definitely irrelevant: The reaction does not conform to the known reaction type of the operation; The patient's clinical status or other treatment methods may produce this reaction, and the disease state may be improved or the reaction may be eliminated by withdrawal of other treatment methods, and present again upon the repeated use of other treatment methods.
- 5) Unable to judge: The reaction is similar to the known reaction type of the operation, and other treatments used at the same time may also cause the same reaction.

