7.1.7.2 Other safety endpoints

- (1) Rate of device-related AEs

Evaluation time: During the trial

Definition of device-related AE: refers to AE that is determined by the investigator to be related, possibly related, unlikely related to the device or the correlation between AE and device is unable to be judge. However, normal postoperative stress reactions, such as fever and constipation, should be distinguished, and those judged by investigators as normal postoperative stress reactions do not need to be recorded in adverse events.

- (2) Rate of SAEs

Evaluation time: During the trial

Serious adverse events refer to events that cause death or serious deterioration of health, including fatal

diseases or injuries, permanent defects of body structure or body functions, hospitalization or prolonged hospital stay, and medical or surgical intervention to avoid causing permanent defects to the body structure or body functions; or that cause fetal distress, fetal death or congenital abnormalities, congenital defects, in the process of the clinical study.

7.1.8 Device deficiency and corresponding evaluation, recording and analyzing method and time:

[figure not shown]
Rate of device deficiencies

Evaluation time: During the operation

Definition of device deficiency: refers to the deficiency of the investigational device which presents in the trial process, such as label error, plastic thread damage, ineffective fastening or release of the locking piece, displacement of shunt blocking membrane, etc.

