According to the summary of the results reported in the literatures, the treatment success rate at 360-day post operation of the ASD closure systems made of traditional metal materials ranged from 93% to 99%, and the rate of common complications during 360-day post operation was between 0.65% and 4.1%. Considering that the ASD closure systems made of traditional metal materials have been on the market for nearly 20 years, the industry has rich interventional experience and the treatment has confirmed efficacy and predictable incidences of common complications. In China, Lifetech Scientific has taken the lead in using absorbable materials that have good biocompatibility to develop novel ASD closure system and applied it for clinic use for the first time. At present, there is still no similar product on the market. Despite the relevant quality control measures, in multi-center clinical trials, there may still be differences in clinical practices (such as interventional techniques and evaluation experience) among different centers, resulting in different effects among different centers, especially the surgeon's learning curves, which will not only affect the proficiency of operations but also the efficacy of the investigational device and the prediction of common complications to a certain extent. In addition, we hope this study can make the clinical efficacy evaluation of the investigational device more realistic, fully understand the differences between the clinical practice of ASD occlusion with novel absorbable materials and the consensus of experts in the ASD occlusion with existing traditional metal occluders, provide objective comparative basis for clinical selection of novel absorbable ASD closure system, and also provide reference for the formulation and standardization of occlusion guidelines with novel absorbable materials in the future. Therefore, according to the results of meta analyses, clinical experience and primary endpoints defined in this trial after full discussion with clinical experts and statistical experts, the target and OPC of Absnow™ ASD closure system are set as follows:

Endpoints	Target	Unilateral boundary value of 95% CI (OPC)
Effective closure rate at 360-day post operation	99%	94%
Rate of common complications during 360-day post operation	1%	6%

Sample size is estimated by SAS9.4 software, and the operation is as follows:

- a) Effective closure rate at 360-day post operation

```
proc power;
onesamplefreq
test = z

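### Protocol 13.1.3 reserves related ratings for reactions already known for the device, so a previously undescribed reaction is rated towards unrelated or fits no category, and can drop out of the SAP's device-related tables

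*Protocol*

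**What the plan says.** **The rating scale.** Protocol 13.1.3 gives five levels for the relation of an AE to the device:

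- "Definitely relevant: The reaction conforms to the known reaction type of the suspected product".
- "Possibly related: The reaction conforms to the known reaction type of the suspected product", with the patient's condition or other treatment as a further possible cause.
- "Possibly irrelevant: The reaction does not quite conform to the known reaction type of the suspected product", with another possible cause.
- "Definitely irrelevant: The reaction does not conform to the known reaction type of the suspected product", with another possible cause and a pattern of improvement when other treatments are stopped and return when they are used again.
- "Unable to judge: The reaction is similar to the known reaction type of the suspected product", with concurrent treatment as another possible cause.

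**The assessor.** The same section opens with "The subject should evaluate the correlation between the AE and test device or operation". Protocol 7.1.7.2 says instead that a device-related AE "refers to AE that is determined by the investigator to be related" or to fall in one of the other levels it lists.

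**The novelty of the device.** Protocol 8.2.1 describes first clinical use and adds: "At present, there is still no similar product on the market".

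**The counting rules.** Protocol 7.1.7.2 counts related, possibly related, unlikely related and unjudgeable events as device-related. SAP 6.1.1 counts possibly, probably and definitely related events as related, groups unlikely related with not related as unrelated, and treats an unclear relationship as related.

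**The concern.** A causality scale for a device in first clinical use should let an assessor rate a reaction as possibly device-related even though nobody has described it before. This one does not. Both positive ratings depend on a match with what is already known, and so does the neutral one. No level uses timing relative to implantation or to the absorption period, and none uses biological plausibility for the device or its degradation products.

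Protocol 5.1 names gradual degradation of the PLLA material as the significant difference from metal occluders. Section 4 reports animal observation for 6 months, while subjects are followed for 5 years. Reactions during later degradation are thus the ones least likely to have a known type to match.

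At stake is the incidence of device-related AEs, listed as an endpoint in Protocol 7.1.7.2 and SAP 3.2.3, together with the device-related SAE summary in SAP 6.1. A rule that steers new reactions towards unrelated biases both downwards.

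**Working it through.** The documents give no figure on this point and no frequency for such reactions, so there is nothing to recompute. The check takes a reaction of a type not yet described for the device, tests it against each level, and then follows it through the two counting rules.

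**Step 1. Which levels are open to an undescribed reaction?**

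| Level in 13.1.3 | Match with known type | Other cause | Open? |
|---|---|---|---|
| Definitely relevant | Must conform | Not mentioned | No |
| Possibly related | Must conform | Also possible | No |
| Possibly irrelevant | Does not quite conform | Possible | Only with another possible cause |
| Definitely irrelevant | Does not conform | Possible, plus withdrawal and recurrence on other treatments | Only with that evidence |
| Unable to judge | Must be similar | Concurrent treatment possible | No |

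Three of the five levels are closed. The two that remain both presuppose another cause.

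**Step 2. Do the documents use one vocabulary?** They do not. Section 13.1.3 has *possibly irrelevant*; Protocol 7.1.7.2 and SAP 6.1.1 have *unlikely related*. SAP 6.1.1 has *probably related*, which neither Protocol section contains. No mapping is given. The trace below assumes that *possibly irrelevant* and *unlikely related* are the same level.

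**Step 3. Where does the event end up?**

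| Undescribed reaction | Rating under 13.1.3 | Protocol 7.1.7.2 | SAP 6.1.1 |
|---|---|---|---|
| A. Another cause is possible | Possibly irrelevant | Device-related | Unrelated |
| B. As A, with withdrawal and recurrence on other treatments | Definitely irrelevant | Not device-related | Unrelated |
| C. No other cause | None fits | Not settled | Related only if recorded as unclear |

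Row A is the main route out of the SAP tables: the same event is counted by one document and not by the other. In row C the SAP's rule for unclear relationships can help, but an assessor who follows 13.1.3 to the letter cannot choose *unable to judge*, because that level requires similarity to a known reaction. Retention then depends on how the form is completed.

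**Step 4. Which outputs use the rating?** The device-related AE incidence and the device-related SAE summary do. The primary safety endpoint is a list of seven named complications (Protocol 7.1.7.1) and the SAE rate is defined by seriousness, so neither uses it. SAP 6.1.1 tabulates all TEAEs by SOC and PT whatever their causality.

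**The case against.** A reader might infer that any new reaction is removed from the device-related AE rate, or that the trial is blind to new signals. The documents do not support either reading.

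- Protocol 7.1.7.2 is deliberately wide. If the two terms are equivalent, a new reaction rated *possibly irrelevant* stays in the Protocol's own rate.
- The SAP counts unclear relationships as related, and a reaction that fits no level is a natural candidate for that rule.
- *Definitely irrelevant* is narrow. Its withdrawal-and-recurrence condition concerns other treatments, not the device, and a true reaction to PLLA would not be expected to show that pattern. Few new device reactions should properly be rated there.
- Some known reaction types exist. Protocol section 4 says PLLA is widely used in other fields and reports the inflammatory reaction in animals; 13.1.4 lists expected events. The Investigator's Brochure and the IFU, which are not among the documents, may say more.
- All AEs must be recorded (Protocol 13.1.2), and unexpected AEs and SAEs are expressly included.
- The sentence that makes the subject the assessor looks like a wording slip, since 7.1.7.2 names the investigator.

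All of this stands as a limit on the consequence. It does not repair the scale. Background knowledge helps with familiar events, not with reactions that nobody has described. The wide Protocol definition does not govern the tables if the SAP grouping is applied. Investigators may use judgement beyond the text, but a plan should not depend on departures from its own criteria.

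**Conclusion.** The point holds as a defect in the rating rule with a limited consequence. Under 13.1.3 as written, an undescribed device reaction cannot be rated definitely relevant, possibly related or unable to judge. With another possible cause it is rated towards unrelated; without one it has no level.

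Such an event can then be missing from the SAP's device-related AE and SAE tables. That step rests on two things: that *possibly irrelevant* is the same level as *unlikely related*, which no text confirms, and that the SAP grouping rather than Protocol 7.1.7.2 is used for the tables. For an uncategorised event it also depends on whether the relationship is recorded as unclear.

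The size cannot be given as a number. The bias is downwards and touches only descriptive summaries; no hypothesis test or success criterion is affected. The change should still be made, because it is cheap and concerns a named safety endpoint of a device in first clinical use.

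**What to change.** In Protocol 13.1.3:

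1. Name the investigator as the assessor, in line with 7.1.7.2.
2. Replace the known-reaction requirement with three criteria: timing relative to implantation or the absorption period; biological plausibility for the device or its degradation products; and presence or absence of another sufficient cause.
3. State that a previously unknown reaction without a more likely alternative cause is rated at least *possibly related*.
4. Remove the similarity condition from *unable to judge*.

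Across Protocol 7.1.7.2, Protocol 13.1.3 and SAP 6.1.1, use one causality scale with the same terms, and one rule for which levels count as device-related. Without this last step, better ratings would still be counted differently in the two documents.

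The cost is rewording, revised guidance on the AE form, and possibly re-rating of AEs already recorded. No new subject data are needed. The reported device-related AE rate may be slightly higher.

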13.1.4 Possible AEs in this trial and corresponding treatments

13.1.4.1 Common complications and corresponding treatments

- (1) Occluder dislocation: Preoperative multi-sectional measurements of ASD size are helpful for selection of indications and occluders. Improper selection of occluder can easily cause dislocation. Through observing the position of the development site and the shape of the left and right discs of the occluder by TTE combined with chest X-ray, it can be judged whether the occluder falls off. If the occluder falls off, it should

be taken out with catcher. If the occluder is large or difficult to take out, the emergency surgery should be performed.

- (2) High-grade atrioventricular block: If degree III atrioventricular block occurs during the operation and is still not recovered after long-term suspension of operation, the interventional therapy should be abandoned; Drug treatment should be given in time if degree III atrioventricular block occurs after operation. The device should be removed by surgery and ASD should be repaired if the drug therapy is ineffective;
- (3) Cardiac tamponade: Cardiac tamponade can be judged by TTE. Emergent pericardial puncture should be performed for blood drainage and decompression to relieve tamponade, temporarily change the hemodynamics, and contend for rescue time. Meanwhile, saline and blood should be infused to correct hemorrhagic shock. Furthermore, emergency thoracotomy exploration should be prepared. Strict anesthesia management is required and cardiac arrest should be strictly prevented. Sufficient blood should be replenished. Blood accumulated in pericardium cavity should be removed during operation. Normal systolic and diastolic function of heart should be restored. Heart damage should be repaired accurately. Close monitoring of cardiac function and rational application of cardiovascular active drugs are required after operation;
- (4) Air embolism: It can be judged by TTE combined with chest X-ray. Oxygen should be inhaled immediately, atropine should be given to patients with slow heart rate, and nitroglycerin should be adopted at the same time to prevent vasospasm;
- (5) Residual shunt above medium: It can be judged by TTE. If the diameter of residual shunt is larger than 5 mm and has hemodynamic significance, it is recommended to block the residual shunt again;
- (6) Intractable headache or migraine: If the subject complains of headache or migraine symptoms, it can be judged according to headache score or MIDAS migraine score: headache score > 2 can be judged as intractable headache, MIDAS migraine score > 1 can be judged as intractable migraine. Corresponding treatments such as hyperbaric oxygenation should be adopted, aspirin should be taken for at least half a year after operation, and anticoagulation therapy can be combined if necessary. (Appendix 2: headache questionnaire and scoring, Appendix 3: MIDAS migraine questionnaire and scoring);
- (7) Cerebral embolism: It can be judged by the clinical manifestations of the subjects with the assistance of brain CT and TTE. The principle of treatment is to improve brain circulation, prevent re-embolism, eliminate brain edema and protect brain function. In acute stage, bed rest should be taken. The respiratory tract should be kept unobstructed and cardiac function should be protected. The nutritional status should be monitored and the balance of water and electrolytes should be kept. Nursing should be strengthened to prevent pneumonia, urinary infection and bedsore. According to the different sources of emboli, symptomatic treatments, including general treatment, surgery, interventional surgery, etc., can be adopted. Relevant surgical guidelines can be referred for operating procedures. Strict anticoagulation during and after operation is the key to prevent embolic events.

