7.1.7.1 Primary safety endpoint: Rate of common complications during 360-day post operation

Note: Common complications include (as shown in the following table)

SN.	Name	SN.	Name
1	Occluder displacement	5	Residual shunt above medium
2	High-grade atrioventricular block	6	Intractable headache or migraine
3	Cardiac tamponade	7	Cerebral embolism

4	Air embolism		
---	--------------	--	--

The definitions of common complications are as follows:

- (1) Occluder displacement: refers to displacement of occluder to right atrium, right ventricular outflow tract, main pulmonary artery, left atrium, etc. due to special anatomical position of ASD, selection of too small occluder resulted from incorrect measurement and improper operation, etc.
- (2) High-grade atrioventricular block: means that there are two or more continuous supraventricular excitations (generally sinus P waves) that cannot be transmitted down to the ventricle at an "appropriate" atrial rate (≤ 135 bpm), and this conduction barrier must be caused by block rather than interference induced by connection or ventricular ectopic pacing points.
- (3) Cardiac tamponade: refers to cardiac compression, ventricular filling obstruction and a series of hemodynamic abnormalities, such as venous pressure increase and even cardiogenic shock, due to the rapid accumulation of fluid in pericardial cavity.
- (4) Air embolism: refers to inadvertently injection of air into coronary artery due to improper operation of occluder implantation. Air embolism can temporarily block blood flow in coronary artery, which may lead to acute myocardial infarction, angina pectoris, arrhythmia and cardiac arrest.
- (5) Residual shunt above medium: left-to-right shunt signal with diameter ≥ 5 mm, judging from Doppler left-to-right signal.
- (6) Intractable headache or migraine: refers to the syndrome with recurrent headache as the main symptom, which may have aura and accompanying symptoms.
- (7) Cerebral embolism: refers to various emboli (such as endocardial mural thrombus, atherosclerotic plaque, fat, etc.) that enter the cerebral artery with blood flow and block blood vessels, which will cause ischemic necrosis of brain tissue in the blood supply area of the artery and result in focal neurological deficit when collateral circulation cannot be compensated.

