Appendix 2: Headache questionnaire and evaluation

This questionnaire is used to express how you feel about headache and the negative impact of headache on your life. Please choose one answer from five choices.

1. When you have a headache, how often does severe pain occur?

A. Never B. Seldom C. Sometimes D. Often E. Always

2. Does the headache limit your ability to daily activities, such as housework, work, school, or social activities?

A. Never B. Seldom C. Sometimes D. Often E. Always

3. Do you often wish to lie down when you have a headache?

A. Never B. Seldom C. Sometimes D. Often E. Always

4. In the past 4 weeks, do you often feel tired due to headache and feel powerless in work or daily activities?

A. Never B. Seldom C. Sometimes D. Often E. Always

5. In the past 4 weeks, do you often feel bored and restless due to headache?

A. Never B. Seldom C. Sometimes D. Often E. Always

6. In the past 4 weeks, have you been unable to concentrate on work and daily activities due to headache?

A. Never B. Seldom C. Sometimes D. Often E. Always

Evaluation:

Choose A: 6 scores, choose B: 8 scores, choose C: 10 scores, choose D: 11 scores, choose E: 13 scores.

Add up the corresponding points for all the answers.

Total score range: 36 - 78

Level 1: ≤ 49 , no or minor impact

Level 2: 50-55, moderate impact

Level 3: 56-59, significant impact

Level 4: ≥ 60 , seriously impact

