Appendix 3: MIDAS Migraine Questionnaire and score

Five questions were asked to assess the time lost (days) due to migraine over a three-month period. The time loss mainly means paid work, household work, family and social activities. The MIDAS score is obtained by adding all days lost.

1. In the past 3 months, how many days have you been unable to go to work or school due to headache?

_____ Days

2. In the past 3 months, how many days have you partially affected your work or study due to headache (efficiency was decreased by more than half)?

_____ Days

3. In the past 3 months, how many days have you been unable to do housework due to headache?

_____ Days

4. In the past 3 months, how many days have you partially affected your housework due to headache (efficiency was reduced by more than half)?

_____ Days

5. In the past 3 months, have you missed visiting friends and relatives, parties, entertainment such as watching TV, playing cards and other similar activities due to headache?

_____ Days

Total days: _____ Days

Score definition of MIDAS Migraine Disability Assessment Questionnaire

Grading	Degree	Disable Level	Suggestion
0-5	I	Slight or infrequent impact	
There is little need for medical intervention. Simple symptomatic treatment can be used with OTC drugs when seizures occur, but the following conditions should be noted:
 
 1. Evaluate the impact of days off due to headache on subjects' life 2. Subjects with infrequent but severe headache need regular treatment 3. Subjects whose headaches are not effectively relieved by painkillers alone need standardized treatment

6-10	II	Mild or frequent impact	Subjects usually have headache for a long time or severe degree, which cannot be completely relieved by analgesic alone and has obvious influence on life. Standardized treatment is needed in the acute phase.
11-20	III	Moderate impact	Headache has serious influence on life. Standardized treatment is needed in the acute phase.
>21	IV	Serious impact	Need preventive treatment.

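### The cut-offs for intractable headache or migraine, a co-primary safety component, are wrong as written: they are stated as scores but fit only the appendices' grades, leaving MIDAS totals of 2 to 5 days in dispute

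*Protocol*

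**What the plan says.** The primary safety endpoint is the rate of common complications over 360 days, and intractable headache or migraine is one of its seven components. Protocol 7.1.7.1(6) defines that component in words only: it "refers to the syndrome with recurrent headache as the main symptom, which may have aura and accompanying symptoms". SAP 3.2.1 names the component without defining it.

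The only numbers are in Protocol 13.1.4.1(6). That item opens "If the subject complains of headache or migraine symptoms, it can be judged according to headache score or MIDAS migraine score" and then sets the rule: "headache score > 2 can be judged as intractable headache, MIDAS migraine score > 1 can be judged as intractable migraine". It refers to Appendices 2 and 3 for the questionnaires and their scoring.

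- Appendix 2 has six questions scored 6, 8, 10, 11 or 13 points each. It states "Total score range: 36 - 78" and groups the totals into four levels. Level 1 is 49 or below, Level 2 is 50 to 55, and the next is "Level 3: 56-59, significant impact".
- Appendix 3 states "The MIDAS score is obtained by adding all days lost" and groups the totals into four degrees. Degree I is 0 to 5 days ("Slight or infrequent impact") and Degree II is 6 to 10 days ("Mild or frequent impact").

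SAP 5.1.2 passes the safety endpoint if the upper limit of the exact two-sided 95% confidence interval is below 6%. SAP 4.2 counts a subject with incomplete 360-day safety follow-up as having had a complication.

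**The concern.** A cut-off of 2 cannot separate anyone on a scale that starts at 36. A cut-off of 1 on the day count labels as intractable a migraine burden that Appendix 3 puts in its mildest band, where it sees little need for medical treatment. Both cut-offs make sense as grades, but the text says score, and each appendix defines its score as something else.

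The same subject could therefore be counted or not, depending on how an investigator or analyst reads one sentence. The endpoint is co-primary and can absorb only a few events, so a few such subjects could matter. In an open single-arm trial, a reading settled after the data are known would be open to challenge whichever way it went.

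**Working it through.** **1. The scales.** The Appendix 2 range reproduces: six lowest answers give 6 × 6 = 36 and six highest give 6 × 13 = 78. Scoring all 5^6 = 15,625 answer patterns puts every one above 2. That includes six answers of Never (36) and six of Seldom (6 × 8 = 48, still Level 1).

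**2. The two readings side by side.**

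| Scale | Cut-off read as a score | Cut-off read as a grade | Where they differ |
|---|---|---|---|
| Headache (> 2) | any completed questionnaire (36–78) | Level 3 or 4: total ≥ 56 | totals 36–55 |
| MIDAS (> 1) | total ≥ 2 days | Degree II or higher: total ≥ 6 days | totals of 2, 3, 4 and 5 days |

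The score reading of the headache cut-off cannot sensibly be applied, so that range is not a practical dispute. For MIDAS both readings can be applied, and they disagree for 2 to 5 days.

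**3. Does other text settle it?** Protocol 7.1.7.1(6) requires recurrence but sets no severity. A subject with recurrent headache and 3 days lost meets it, and is then a complication under one reading and not under the other. Neither document says that score means Level or Degree.

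**4. The margin in the endpoint.** The protocol's sample size reproduces (Protocol 8.2.1: target 1%, limit 6%, one-sided 0.025, power 80%):

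n = [(1.960 × √(0.06 × 0.94) + 0.842 × √(0.01 × 0.99)) / 0.05]² = 120.65, rounded up to 121; 121 × 1.2 = 145.2, rounded up to 146.

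The cut-offs do not enter this calculation. SAP 3.1 plans 142 subjects.

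The exact upper limit for x events in N subjects is the 97.5% quantile of a Beta(x + 1, N − x) distribution:

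| N | Most events that pass | One more event |
|---|---|---|
| 142 (SAP) | 2: upper limit 5.00% | 3: 6.05%, fails |
| 146 (protocol) | 3: upper limit 5.89% | 4: 6.87%, fails |

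More generally, at most 2 events pass for N from 118 to 143, and at most 3 for N from 144 to 167. At the 1% target the expected count over all seven components is 142 × 0.01 = 1.42 or 146 × 0.01 = 1.46.

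**5. Imputation uses the same allowance.** Under SAP 4.2, 3 incomplete subjects of 142 (2.1%) or 4 of 146 (2.7%) fail the analysis in the full analysis set with no real complication at all.

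**The case against.** The strongest reply is that context resolves the sentence. The headache cut-off can only be a Level. The MIDAS cut-off is in the same sentence, uses the same word, and points to a table that also has four grades. The day-count reading would also send a subject whom Appendix 3 says needs little treatment towards hyperbaric oxygen. This stands as far as it goes: the grade reading is the more likely one for both scales. But it is an inference set against Appendix 3's explicit definition of the MIDAS score as days, and a co-primary endpoint should not depend on it.

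Second, the cut-offs are in the section on handling complications, are worded permissively and apply only after a complaint, while the endpoint is defined in 7.1.7.1. That narrows the group affected: a subject must complain, have recurrent headache and total 2 to 5 days. It does not remove the problem, because 13.1.4.1 lists the same seven complications and holds the only threshold in either document. Permissive wording leaves more discretion, not less.

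Third, case report form instructions or site training may already fix the reading. They are not in the documents, so this cannot be excluded. The rule still belongs in the protocol and SAP.

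Fourth, imputation could make the matter moot. The protocol allows for up to 20% dropout, and step 5 shows that far less is enough to fail the test. So this cut-off can decide the full-analysis-set result only if follow-up is nearly complete. That is correct and limits the practical weight of the point.

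**Conclusion.** The stated cut-offs are wrong as written and should be corrected. That conclusion rests on the protocol's own text and simple arithmetic, and confidence in it is high. The effect on the result is unknown: the documents give no headache or migraine rate, so the number of subjects at 2 to 5 MIDAS days cannot be estimated. What is known is that the allowance is 2 events at 142 or 3 at 146, assuming all planned subjects enter the full analysis set.

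Two stronger readings are tempting and are not supported.

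- A reader might infer that the device could be declared safe in error. The literal reading counts more complications than the grade reading, so the error runs the other way.
- A reader might take the chance of sitting exactly at the limit as the chance that this defect changes the result. At a true 1% rate and complete follow-up, that chance is 24.5% for exactly 2 of 142 and 12.1% for exactly 3 of 146. These figures describe the margin of the whole composite and would be the same for an ambiguity in any component. A changed result also needs a subject in the disputed band who is classified differently, and no figure exists for that.

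**What to change.** Ask the clinical team to confirm what was meant, without reference to the scores of subjects already followed. Then replace the cut-offs in Protocol 13.1.4.1(6) with Level 3 or higher (Appendix 2 total of 56 or more) and Degree II or higher (MIDAS total of 6 or more days). Use the same wording in Protocol 7.1.7.1(6) and in the SAP's definition of the primary safety endpoint, and keep the requirement for recurrent headache. The item in 13.1.4.1 also introduces treatment, so the team should check that the restated cut-offs suit that use.

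The cost is a wording amendment in three places, with the ethics committee approval that Protocol 12.2 requires for any protocol change. No visit, test or sample size changes.
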